## **6. INCLUSION AND EXCLUSION CRITERIA\***

### **Participant inclusion/exclusion:**

Inclusion criteria:

- (1) Age 18-50
- (2) Singleton or multiple pregnancies
- (3) English or Spanish speaking
- (4) Diagnosis of Chronic hypertension (8-26 weeks gestational age) or gestational hypertension (20-26 weeks gestational age)
- (5) A patient of the UMass Memorial Health OB/MFM clinics in Worcester, MA
- (6) Willing to share HBPM data
- (7) Comfortable with the use of smartphones and mobile apps

Exclusion criteria:

- (1) Severe HTN (BP greater than or equal to 160/110mmHg at the enrollment visit)
- (2) Current diagnosis of preeclampsia
- (3) Active substance use
- (4) Serious physical illness or any illness that makes them unable to interact with a smart device
- (5) Enrolled in another HBPM program
- (6) Excluded from study participation by their provider
- (7) Inability to provide informed consent

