Participant data will be collected at baseline (study entry) and the 8-wk follow-up in the privacy of the OB/MFM office (before or after clinic visits). Participants will be asked about their age, ethnicity/race, medication use, baseline HBPM use, and health literacy. If the 8-wk follow-up cannot be scheduled in person, this will be conducted over the phone or over Zoom. All 4-week follow-up visits will be done through a phone check-in. Study staff responsible for outcome assessment will be blinded to group assignments. Assessments will be pre-tested to ensure the time burden does not exceed 30 minutes.

**Post-intervention focus group:** After completing the 8-wk pilot test, three participant focus groups (intervention arm only, N=5/group, 1–1.5-hours) will discuss their experience and barriers/facilitators to engagement with Moms@Home.

Two focus groups with providers (N=5/group for a total of 10 providers, 1-hour) will focus on the home BP report experience, with one group of low utilizers and a second group of high utilizers of the electronic health record HBPM reports. Verbal consent for providers interested in focus group participation will be documented in Redcap.

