#### **13. DATA ANALYSIS AND MANAGEMENT**

##### **Provide a power analysis and/or support for the sample size proposed for this study**

Power calculations for this pilot trial are based on a 2-group, 2-sided Chi-square test of proportions with alpha=0.05. Assuming the intervention will improve HBPM adherence from 10% to 35% (based on our prior work with non-pregnant adults with HTN), we will achieve 80% power when the sample size is 43 per arm (N=86). We will recruit 100 participants to account for ~15% attrition. We base our proposed sample size also on pragmatic considerations related to recruitment, retention, and our focus on feasibility, providing important information for design and recruitment for a future R01 to test Moms@Home in a large RCT.

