## **INVESTIGATOR STUDY PLAN – Moms@Home**

### **V1.0**

#### **Describe the data analysis plan, including any statistical procedures**

We will compare HBPM adherence (primary outcome) between the two arms (Moms@Home and ESC). Other outcomes (see section 10) will be compared using generalized estimating equations accounting for the appropriate distribution (e.g., binomial — dichotomous outcome such as HBPM adherence, or Poisson/Negative Binomial — count). We will quantify missing data and dropouts and examine reasons for ineligibility and discontinuation. All data distributions will be examined, and summary statistics calculated by group using an intention-to-treat approach. We will also include other potential modifiers of the intervention effect, potential confounders, and other covariates of interest. In the event of possible effect modification, we will explore the nature of the relationship through the use of interaction terms and subsequent subgroup analysis. This approach will be used for measures with pre-post measurements as well as those collected post-implementation only. Although the pilot study may not have adequate statistical power for testing our hypotheses of improved BP control and medication adherence, we will conduct an exploratory analysis of any treatment effects. We will also examine HBPM adherence by race/ethnicity. Per-protocol analysis will also be performed using all data available from randomized participants without replacement of missing data. Goal attainment scaling, step count, and sleep duration will be characterised for each participant, and then compared between the Moms@Home and ESC groups using a Wilcoxon-Mann-Whitney rank-sum test. In an exploratory analysis, we will compare HBPM, BP control, activity, frequency of visits, and pregnancy outcomes between the primary groups and subgroups (stratified by race/ethnicity, health literacy, income level, age, obesity, and trimester). Qualitative analyses will use applied thematic and content analysis for post-intervention focus groups. All quantitative analyses will be conducted using SAS 9.4 or STATA version 18. We will estimate relevant parameters including estimates of trial retention, intraclass correlation coefficient, standard deviation, and effect size for future R01 power calculations.

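### The primary adherence comparison does not commit to adjusting for baseline home-monitoring use or for clinic; naming both in advance is nearly free and brings a modest gain.

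*Protocol*

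**What the plan says.** Only the protocol is at hand.

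- **Primary comparison.** The data analysis plan in section 13 says: "We will compare HBPM adherence (primary outcome) between the two arms (Moms@Home and ESC"). It names no test, model or covariate for this comparison.
- **Sample size.** The power paragraph in section 13 is "based on a 2-group, 2-sided Chi-square test of proportions with alpha=0.05", for 10% against 35% adherence, giving 43 per arm. It adds: "We will recruit 100 participants to account for ~15% attrition".
- **Covariates.** After assigning generalized estimating equations (GEE) to the other outcomes, section 13 says: "We will also include other potential modifiers of the intervention effect, potential confounders, and other covariates of interest". No variable is listed.
- **Baseline data.** Section 11 says: "Participants will be asked about their age, ethnicity/race, medication use, baseline HBPM use, and health literacy".
- **Randomisation.** Section 11 stratifies the permuted blocks by clinic, and four clinics take part. Prior HBPM use is not a stratum.
- **Eligibility.** Section 6 excludes women "Enrolled in another HBPM program". Women who measure their own pressure outside a program can enter.
- **Subgroups.** The exploratory strata in section 13 are race/ethnicity, health literacy, income, age, obesity and trimester. Prior HBPM use is not among them.

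**The concern.** The protocol collects the entry value of the behaviour that it later uses as its primary outcome, but commits to no use of it in the design or the analysis. Women who already measure their pressure at home may well adhere better whichever arm they join. With about 43 per arm they can fall unevenly between arms by chance, and an unadjusted difference carries that imbalance into the realised estimate. Variance that the baseline value could explain stays in the standard error. Clinic, which restricts the randomisation, has no stated place in the primary analysis either.

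The general covariate sentence does not settle this. If it does not reach the primary outcome, nothing is adjusted for. If it does, the choice of covariates is open and could be made after the data are seen. Planned power is only about 80%, and section 13 intends the effect-size estimate to feed the power calculation for a larger trial, so the precision of this one estimate matters.

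**Working it through.** **1. The plan's own figure.** Inputs from section 13: p0 = 0.10, p1 = 0.35, two-sided alpha 0.05, power 80%. The mean proportion is 0.225.

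n = [1.96·√(2·0.225·0.775) + 0.842·√(0.10·0.90 + 0.35·0.65)]² / 0.25² = (1.157 + 0.474)² / 0.0625 ≈ 42.6, so 43 per arm. Power at 43 is 0.804. The stated figure reproduces.

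**2. Assumptions.** The protocol gives neither the share q of prior self-monitors nor their adherence gap g over non-users. I take q = 20-30% and g = 10, 20 or 30 points.

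**3. Chance imbalance.** SD = √(2q(1−q)/43).

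- q = 0.20: √(0.32/43) = 0.086
- q = 0.30: √(0.42/43) = 0.099

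At q = 0.30 the chance of an imbalance above 10 points is about 31%.

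**4. Shift in the realised difference per SD of imbalance** (SD × g):

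| g | q = 0.20 | q = 0.30 |
|---|---|---|
| 10 points | 0.9 points | 1.0 points |
| 20 points | 1.7 points | 2.0 points |
| 30 points | 2.6 points | 3.0 points |

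**5. Variance that adjustment removes.** The unadjusted variance term is 0.10·0.90 + 0.35·0.65 = 0.3175. With the same gap in both arms, the share removed is 2q(1−q)g²/0.3175:

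| g | q = 0.20 | q = 0.30 |
|---|---|---|
| 10 points | 1.0% | 1.3% |
| 20 points | 4.0% | 5.3% |
| 30 points | 9.1% | 11.9% |

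Simulation at 43 per arm, adjusting for prior use and four clinics, gave cuts of under 1%, about 4-6% and about 10-12% for the three gaps.

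**6. Power.** Simulated trials (4,000 per scenario, q = 0.30, linear risk model with robust standard errors, adjusting for prior use) gave:

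- 10-point gap: 82.6% to 83.0%
- 20-point gap: from 82-84% to 84-85%
- 30-point gap: from 82-84% to 87-89%

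**7. How plausible is the top of the range?** Hold control adherence at 10% with q = 0.30. Non-users are then at 0.10 − 0.3g, and users are g higher.

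- g = 0.10: 7% vs 17%, odds ratio 2.7
- g = 0.20: 4% vs 24%, odds ratio 7.6
- g = 0.30: 1% vs 31%, odds ratio about 44

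The 30-point case is therefore an upper bound.

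**8. A second parameterisation.** With a common odds ratio of 2, 4 or 8 and q = 20-50%, variance falls by about 2%, 7-8% and 15-17%. A Mantel-Haenszel test stratified by prior use has power 0.82, 0.83-0.85 and 0.86-0.88, against 0.81-0.83 unadjusted.

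**9. Validity and downside.** The unadjusted test's simulated type I error was 0.05-0.06 throughout, whether or not prior use predicted adherence. If prior use is unrelated to adherence, stratifying by it costs about 1 point of power, and adjusting for prior use plus four clinics costs up to about 3 points. Expected adherent women: 43·0.10 + 43·0.35 = 4.3 + 15.05 ≈ 19.

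**The case against.** The strongest reply has three parts.

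**Covariates are not excluded.** Section 13 promises them. Its GEE sentence gives HBPM adherence as an example of a dichotomous outcome, and a later line extends the approach to measures collected only after the intervention. A reader might infer that the plan leaves baseline HBPM use out of the primary analysis. The text does not support that: the variable is not named, and it is not ruled out. This part stands, and the point is worded accordingly.

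**A covariate list commonly belongs in a statistical analysis plan**, which is not shown. This also stands, in that the absence of a list is not itself an error. What remains is in the text shown: section 13 names methods for other outcomes, leaves the primary comparison as a bare contrast, and adds an open-ended covariate sentence whose reach is unclear.

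**The harm is small.** A reader might infer that the unadjusted result would be biased or its test invalid. It would not be: randomisation keeps it unbiased on average, its standard error already allows for chance imbalance, and its type I error does not rise with the prognostic strength of prior use. A reader might also take a variance cut of 11-12%, or a gain of some 4-6 points of power, as what to expect. That needs a control-arm odds ratio of about 44 at 30% prior use. With a 20-point gap the gain is 1-2 points. The exclusion of women in another HBPM program may also reduce the number of prior self-monitors.

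**Conclusion.** The point holds as a recommended clarification of modest size. The protocol commits neither to baseline HBPM use nor to clinic in the primary comparison, and its general covariate sentence leaves the choice open. The unadjusted analysis is valid and the sample size reproduces, so no conclusion of the trial is threatened.

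What is at stake is precision and the closeness of one realised estimate: about 1-3 points per SD of imbalance against a planned 25, and about 1% to 12% of the variance. These sizes rest on assumed values of 20-30% prior self-monitors and a 10- to 30-point adherence gap, neither of which the protocol gives. The lower and middle parts of the range are the more plausible.

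**What to change.** Add to section 13 that:

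- the primary arm difference is estimated with prespecified adjustment for baseline HBPM use and clinic, and nothing else;
- it is reported as a standardised risk difference with 95% CI, or a standardised mean difference if adherence is analysed as the proportion of expected readings;
- the unadjusted comparison is supportive;
- analyses with any other covariate are exploratory, so that the general covariate sentence no longer bears on the primary result.

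Also state in section 11 that baseline HBPM use is recorded before the allocation is revealed. The section places randomisation after consent but does not say whether the baseline questions come first.

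The cost is a few sentences, with no new data, visits or participants. The statistical price is about 1-3 points of power if prior use turns out not to be prognostic. With only about 19 adherent women expected, the covariates must stay few.

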#### **Describe any procedures that will be used for quality control and data security of collected data**

- Principles underlying our approach to quality control include: (1) standardization of measurements and interventions; (2) use of clear and specific protocols for all activities, including training for data collection, intervention, and data processing; (3) validation and verification of all data collection and management procedures through data editing, double entry of data, bias detection (e.g., digit preference or unexpected runs) and use of software capable of checking for out-of-range values and other sources of outliers; (4) implementation of a data cleaning protocol which includes checks for consistency and examinations of frequency tabulations; and (5) regular meetings and progress reports to provide specific, well-documented feedback to the project personnel concerning potential difficulties as well as sufficient follow-up to ensure that problems are resolved in a timely fashion. Any changes to data sets resulting from these queries will be recorded through an electronic audit trail.

All data activities will occur in the context of reproducible research. Specifically, datasets and analyses will be generated under documented protocols and standard operating procedures that allow other investigators to replicate findings. All variables will have

## **INVESTIGATOR STUDY PLAN – Moms@Home**

### **V1.0**

descriptive names and statistical programs will be annotated and archived, with the goal of making it easy to generate (and reproduce) research products.

Computerized data forms and other records will be kept in UMass Chan Redcap and a network QMC drive behind its firewall, where access is restricted to authorized personnel (with access through network username and password). Backup paper copies kept in a separate, secure location in locked cabinets in locked offices accessible only to research staff. Electronic data back-ups will be performed at least daily. To protect against inappropriate access, we will first handle and transmit only de-identified data wherever possible. Data transmissions will be handled over secure VPN connections or other secure procedures, and data will be encrypted wherever feasible. Analytic datasets will be stripped of patient identifiers, with re-identifying master lists kept in a separate, secure place.

- FitBit will have access to participant data from device (i.e. daily step count, heart rate and sleep data). When participant sign up for their FitBit account, they will agree to a privacy policy (see here : [Fitbit Legal: Privacy Policy](#)). Each participant will be assigned a study ID and a study Fitbit login so that data is de-identified on export. FitBit is considered HIPAA approved and all information collected from device will remain confidential and will remain on secure servers.

#### **14. PROVISIONS TO MONITOR THE DATA TO ENSURE THE SAFETY OF SUBJECTS**

This study has minimal risks to subjects and adverse events are not anticipated, therefore, there is no data safety committee.

Study staff will monitor the Moms@Home platform twice daily and receive alerts for abnormal values (BP >140/90 mmHg). Study staff will call participants after the alert to ensure they reached the healthcare team or to direct participants to labor and delivery for severe elevations (BP >160/110 mmHg) or BP >140/90 mmHg with any preeclampsia symptoms. Similarly, we may encounter low BPs. For symptomatic systolic BP <90 mm Hg or DBP <50 mm Hg, participants will be instructed to call their OB/MFM office (symptoms, e.g., lightheaded, faint, experiencing vision changes, etc).

As is the current practice in the OB/MFM clinics, out of range blood pressures in the ESC group will be the responsibility of the participant to communicate them to their OB/MFM team. All participants will be given the phone number for the research staff to call in case there are questions about HBPM measures during business hours. Outside of business hours, the ESC participants will be instructed to report abnormal values by making a phone call or Epic MyChart message to their OB/MFM caregivers.

To protect participants against the risk of loss of confidential information, data abstractors will not be allowed to create or keep any other data records besides the formal records that will be created in the electronic data capture systems. We will obtain only the most limited personal identifiers as needed to accomplish the follow-up contact goals of the study, including patient name, email address, and other necessary information.

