## **INVESTIGATOR STUDY PLAN – Moms@Home** **V1.0**

With regards to confidentiality, all patient data will be stored on a secure server accessed via encrypted devices only. All records with personal identifiers will be destroyed 6 years after completion of the study by shredding of the hard paper copy and destruction of the electronic files. Any participant with severe hypertension (described above in exclusion) will not be eligible for this study, and the participant's primary Obstetrician or MFM will be notified of the severe range blood pressure.

Although our study poses minimal risk to subjects and no adverse events are expected due to the nature of the study, we will follow the adverse event procedure of the UMass Chan Medical School. The current guidelines require that items meeting the criteria of prompt reporting (ex. harm experienced by a participant that is unexpected and probably related) will be reported to the IRB within 5 business days of the investigator becoming aware of the event.

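### Protocol section 6 counts a BP of exactly 160/110 mmHg as severe, but the staff action rule in section 14 starts only above it

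*Protocol*

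**What the plan says.** Section 6, first exclusion criterion: "Severe HTN (BP greater than or equal to 160/110mmHg at the enrollment visit". The limit is inclusive.

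Section 14 sets the staff rule for home readings on the Moms@Home platform. Staff "receive alerts for abnormal values (BP >140/90 mmHg"). The response to an alert is graded:

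- "Study staff will call participants after the alert to ensure they reached the healthcare team"; or
- "direct participants to labor and delivery for severe elevations (BP >160/110 mmHg"), "or BP >140/90 mmHg with any preeclampsia symptoms".

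Here the severe limit is strict.

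Later in section 14 the eligibility rule is restated: "Any participant with severe hypertension (described above in exclusion) will not be eligible for this study". The woman's obstetrician or MFM physician "will be notified of the severe range blood pressure". This brings the inclusive definition of section 6 into section 14.

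The staff rule covers the Moms@Home arm only. Women in the enhanced standard care arm report out-of-range values to their own obstetric team.

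**The concern.** The protocol uses the word severe, with the same pair of numbers, under two different inequalities. Section 14 contains both: the inclusive one by reference to the exclusion criteria, and the strict one in the staff rule. A reading that is severe enough to keep a woman out of the trial is therefore not severe once she is in it.

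This threshold chooses between two actions. On one side staff make a call; on the other they send the participant to labor and delivery. The protocol has no data safety committee and lists its safety endpoints as not applicable, so this rule is the main staff escalation step it describes for home readings. Its limit should have one meaning.

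**Working it through.** The protocol states no figure to reproduce here. The check is to apply both limits to readings at and around the boundary.

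**Inputs**

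- Exclusion limit: ≥160/110 (section 6).
- Staff limit for severe elevations: >160/110 (section 14).
- Alert limit: >140/90 (section 14).
- Second route to labor and delivery: >140/90 with any preeclampsia symptom (section 14).

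**At exactly 160/110**

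- Section 6: 160 ≥ 160 and 110 ≥ 110 are both true, so the reading is severe.
- Section 14 staff rule: 160 > 160 and 110 > 110 are both false, so it is not severe.
- Alert: 160 > 140 and 110 > 90 are both true, so the alert and the call apply.

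The result at this value is the same whether the slash means 'and' or 'or'.

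**Readings around the limit, with the slash read as 'or'**

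| Reading | Severe in section 6 (≥) | Severe in section 14 staff rule (>) | Alert (>140/90) |
|---|---|---|---|
| 159/109 | no | no | yes |
| 160/100 | yes | no | yes |
| 150/110 | yes | no | yes |
| 160/110 | yes | no | yes |
| 161/100 | yes | yes | yes |
| 161/111 | yes | yes | yes |

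The readings that are severe under ≥ but not under > are those with systolic exactly 160 and diastolic at most 110, or diastolic exactly 110 and systolic at most 160. Each of these has systolic above 140 or diastolic above 90, so the alert always fires. If the woman has preeclampsia symptoms, the second route sends her to labor and delivery anyway. What is lost is the direction to labor and delivery for a woman without symptoms.

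**Effect of the slash notation**

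Read as 'and', 160/100, 150/110 and 161/100 are not severe under either limit, and only 160/110 in the table separates the two. The slash thus leaves a second ambiguity, which the correction can remove at the same time.

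**Reach**

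About 100 women are to be enrolled. With equal allocation (assumed), about 100 / 2 = 50 fall under the staff rule. The protocol gives no distribution of home BP, so the number of affected readings cannot be estimated.

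**The case against.** The two limits serve different purposes. Section 6 decides eligibility from a reading at the enrollment visit, section 14 triages home readings, and nothing in the protocol says that the exclusion cut-off governs triage. When a boundary value occurs at enrollment, the stated response is to notify the obstetrician or MFM physician, not referral to labor and delivery. When it occurs at home, staff call to make sure the participant has reached her care team. Either way the obstetric team can escalate. The staff rule also uses a strict sign for all its high-BP limits, which may be shorthand rather than a chosen threshold. Finally, the colour-coded action limits taught to participants are not shown in the protocol and may already include the boundary value.

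Much of this stands. It shows that the gap in care is narrow, that the strict sign may well be unintended, and that what a participant would do herself is unknown. It does not remove the inconsistency. Both rules use the word severe at 160/110, and section 14 itself borrows the inclusive definition. If the difference is deliberate, it needs a stated reason. If it is shorthand, the sign should be corrected, because the written rule then omits its own severe-range action at a value the protocol calls severe.

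**Conclusion.** The point holds: the staff rule in section 14 is wrong as written at the limit. It is a minor correction to a safety threshold that should be made. It affects one whole-mmHg value per component, in women without symptoms, in the Moms@Home arm only, and the alert and call remain in place.

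The mismatch follows from the text alone. The list of affected readings assumes whole-mmHg values and the slash read as 'or'; the mismatch at 160/110 itself does not depend on how the slash is read. The practical consequence assumes that staff follow the written rule and do not escalate on their own judgment. Nothing in the endpoints, sample size or analysis is touched.

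**What to change.** In the section 14 staff rule, define severe elevations as *systolic ≥160 or diastolic ≥110 mmHg*. The same paragraph already gives its low limits by component, "For symptomatic systolic BP <90 mm Hg or DBP <50 mm Hg", so the form is familiar. Mirror the wording in the section 6 exclusion criterion so that the two sections read alike. If a higher limit for home readings is really intended, keep it, call it something other than severe, and give the reason.

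Then check that the colour-coded action limits, the FAQ sheet and the HBPM pamphlet (section 11) use the same cut-off wherever they state one.

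The cost is one phrase in section 14 and a matching one in section 6. The FAQ sheet and pamphlet have yet to be written and submitted to the IRB, so they can carry the corrected limit from the start.

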#### **Study arms:**

**Moms@Home intervention arm:** Participants randomized to Moms@Home will receive the Moms@Home app ( $\pm$  Samsung smartphone), the digital BP monitor and cuff, and FitBit activity tracker. An orientation, FAQ sheet and HBPM pamphlets will include HBPM instructions, safety protocols, an introduction to the app, and tech support for the digital BP monitor, app, and FitBit. The FAQ sheet and HBPM pamphlet will be generated and submitted through a later modification of the IRB for approval before use. Participants randomized to the Moms@Home intervention arm will be helped by research staff to download and set up the MDH app and will be provided with a Bluetooth enabled blood pressure cuff and a FitBit that syncs with MDH .

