## **INVESTIGATOR STUDY PLAN – Moms@Home**

### **V1.0**

Participants in the Moms@Home arm who do not have a smartphone, or have a limited data plan and prefer a study phone will be provided with a study smartphone, which they will return after their time on the study. Participants will each select personalization for daily notifications and set one personal goal. Participants will also be reminded to take daily home blood pressure measurements to be synced into the app.

**Enhanced Standard Care (ESC) arm:** Participants randomized to Enhanced Standard Care (ESC) will receive the digital BP monitor and cuff, a paper diary to record BP values, and a FitBit activity tracker. A modified orientation and FAQ sheet will include the same HBPM instructions, safety protocols, and tech support for the digital BP monitor and FitBit. Participants will each set one personal goal. Participants will also be reminded to take daily home blood pressure measurements to be recorded in the paper diary.

At home, over the 8-week RCT, participants will be instructed to measure their BP daily (2 readings, separated by 1 min) after a 3 min rest period. An HBPM video for reference will be part of the Moms@Home portal. The Moms@Home portal can be programmed with English or Spanish as default language and all videos will have Spanish subtitles. Traffic light (red, yellow, green) alerts and actions for abnormal BP values will be reviewed using a teach-back method. Participants will also be instructed to wear the study FitBit for daily activity and heart rate monitoring. Data from the FitBit will be transmitted through the MDH app to the study team for participants randomized to the intervention arm. For participants who are randomized to the enhanced standard care arm, de-identified physical activity i.e. daily steps, heart rate data and sleep data will be collected via encrypted methods through the FitBit app. Staff will be able to confirm data transmission prior to the participant heading home. The research team will call participants 1–3 days after their scheduled start to address any concerns, ensure data capture, and provide tech support.

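### Section 14 lets Enhanced Standard Care (ESC) women report any abnormal reading out of hours by portal message, without limiting that route to non-severe, asymptomatic readings

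*Protocol*

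**What the plan says.** Four parts of section 14 bear on this.

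- **App arm, high readings.** Staff check the Moms@Home platform twice a day and receive alerts above 140/90 mmHg. They then phone the participant to confirm that she reached her care team, or "to direct participants to labor and delivery for severe elevations (BP >160/110 mmHg) or BP >140/90 mmHg with any preeclampsia symptoms".
- **Low readings.** "For symptomatic systolic BP <90 mm Hg or DBP <50 mm Hg, participants will be instructed to call their OB/MFM office". A portal message is not offered.
- **ESC, responsibility.** In line with current clinic practice, "out of range blood pressures in the ESC group will be the responsibility of the participant". The research phone number, given to everyone, is for questions in business hours.
- **ESC, out of hours.** "Outside of business hours, the ESC participants will be instructed to report abnormal values by making a phone call or Epic MyChart message", addressed to the OB/MFM caregivers.

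Section 11, under the study arms, describes participant teaching. For the app arm: "An orientation, FAQ sheet and HBPM pamphlets will include HBPM instructions, safety protocols". For ESC: "A modified orientation and FAQ sheet will include the same HBPM instructions, safety protocols, and tech support". In a paragraph not limited to one arm: "Traffic light (red, yellow, green) alerts and actions for abnormal BP values will be reviewed using a teach-back method". The cut-offs for the colours and the action for red are not given. Section 11 also says that the FAQ sheet and pamphlet will go to the IRB later.

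**The concern.** The out-of-hours sentence is a planned instruction to participants, and it covers abnormal values without grading them. A woman with a severe reading, or a raised reading with symptoms of preeclampsia, who sends a MyChart message at night has done what the sentence asks. The section treats the same readings as urgent when staff see them in the app arm.

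ESC women keep a paper diary, so no platform alert arises for them, and section 14 describes no other staff check on their readings out of hours. The wording of the instruction therefore carries more weight in ESC than in the app arm. What is at stake is participant safety. HBPM adherence, the comparison between arms and the sample size are not involved.

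**Working it through.** No arithmetic applies: the point depends on no rate, power or sample size. The check is a reading of section 14 in full, followed by a search of the rest of the protocol for a rule that would limit the message option.

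**Step 1. Set the instructions side by side.**

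| Reading | Who acts under section 14 | Route stated |
|---|---|---|
| Above 160/110 mmHg, app arm | Staff, after a platform alert | Labor and delivery |
| Above 140/90 mmHg with preeclampsia symptoms, app arm | Staff, after a platform alert | Labor and delivery |
| Symptomatic low BP | Participant | Phone call to the OB/MFM office |
| Abnormal value, ESC, out of hours | Participant | Phone call or MyChart message |

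Only the last row offers a message, and it has no severity limit.

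**Step 2. Does the last row include severe readings?** Section 14 gives no ESC threshold for an abnormal value. The 140/90 mmHg figure defines the platform alert, so carrying it over to ESC is an inference. The argument does not need it: a reading above 160/110 mmHg is abnormal on any reasonable definition, and nothing in the sentence removes it.

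**Step 3. Is there a limit elsewhere?**

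- Section 14 later says that the participant's "primary Obstetrician or MFM will be notified of the severe range blood pressure". That concerns women found ineligible because of severe hypertension, not readings during follow-up.
- Section 6 excludes women at or above 160/110 mmHg, but only at the enrollment visit. Section 14 itself plans for severe readings afterwards.
- Section 11 has the shared safety protocols and the traffic-light actions. These could supply the limit, but their content is not stated and section 14 does not point to them.

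**Step 4. What follows.** The protocol as printed contains no text that restricts the message option. Whether the participant materials restrict it cannot be settled from this document.

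**Size.** The instruction applies to the whole ESC arm, about 100 / 2 = 50 women. How many of them would have a severe or symptomatic reading out of hours cannot be estimated, because the protocol gives no rate for such home readings and does not define business hours.

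**The case against.** The strongest reply is that severity-graded teaching is already planned. Section 11 gives ESC the same safety protocols and reviews red, yellow and green actions by teach-back. A three-level scheme is where an urgent step would normally sit. This stands as a limit: the protocol does not show that ESC women lack an urgent instruction, and a reader should not infer that they do.

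A reader might also infer that section 14 contradicts section 11, or contradicts itself. The text does not support that. The ESC sentence governs how a value is reported. It does not say that a message replaces seeking care, and a woman can do both. The phone call is also listed first. The labor-and-delivery text is a staff action after an alert, and section 14 gives no labor-and-delivery instruction addressed to the participant in either arm. So this is not a safeguard written for app-arm participants and withheld from ESC participants.

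Self-reporting is described as current clinic practice, which suits a standard-care comparator. That explains who is responsible for reporting. It does not explain why a message should suffice for a severe reading.

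Finally, the protocol says nothing about how quickly portal messages are read. Slow reading at night or on weekends is an assumption.

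What survives is narrow: a stated instruction leaves a message open as the sole report of a reading that the same section treats as urgent.

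**Conclusion.** The point holds as a safety clarification, at the low end of what should be fixed. Section 14 does not limit the MyChart option to non-severe, asymptomatic readings, and it does not refer to the material in section 11 that might do so. Harm is possible but not shown, and no event count can be given. The practical importance rests on two things outside the document: that out-of-hours messages may wait before being read, and that the traffic-light actions do not already direct ESC women to urgent care. If those actions do, the change only brings section 14 into line with them. Confidence is moderate. The statistical comparison is not affected.

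**What to change.** In section 14, reserve MyChart messages for readings that are neither severe nor accompanied by symptoms, and add one sentence for both arms, for example:

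*At any hour, a reading above 160/110 mmHg, or above 140/90 mmHg with any preeclampsia symptom, means going to labor and delivery or phoning at once; a portal message is not enough.*

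Cross-refer this to the red-zone action in section 11, and use the same wording in the FAQ sheets and the HBPM pamphlet. The obstetric investigators should set the final text. Staff review of synced readings stays in the app arm only, so the contrast between arms is preserved.

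The cost is one or two sentences, a cross-reference and matching handout text, which can go with the IRB modification already planned for the handouts. No patients, staff or procedures are added. The downside is a few more out-of-hours calls or visits, for readings that the protocol already treats as urgent.
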